Appendix E: Intraoperative assessments

Subject ID:	Date:	Time:	Interviewer:
-------------	-------	-------	--------------

Time of speculum insertion: ____:____ AM/PM

1) After speculum placement.

How much pain are you experiencing right now? (make an X on the line)

very little _____ very much

- Patient unable to complete VAS due to sedation and seems comfortable Yes No
- Patient unable to complete VAS due to sedation and seems uncomfortable Yes No
- Patient refuses to complete VAS and seems comfortable Yes No
- Patient refuses to complete VAS and seems uncomfortable Yes No

2) During uterine aspiration.

How much pain are you experiencing right now? (make an X on the line)

very little _____ very much

- Patient unable to complete VAS due to sedation and seems comfortable Yes No
- Patient unable to complete VAS due to sedation and seems uncomfortable Yes No
- Patient refuses to complete VAS and seems comfortable Yes No
- Patient refuses to complete VAS and seems uncomfortable Yes No

Time of speculum removal: ____:____ AM/PM

3) After speculum removal.

How much pain are you experiencing right now? (make an X on the line)

very little _____ very much

- Patient unable to complete VAS due to sedation and seems comfortable Yes No
- Patient unable to complete VAS due to sedation and seems uncomfortable Yes No
- Patient refuses to complete VAS and seems comfortable Yes No
- Patient refuses to complete VAS and seems uncomfortable Yes No

4) 3-5 minutes after procedure completion.
What was the maximum pain you experienced during your abortion?
(make an X on the line)

very little _____ very much

- Patient unable to complete VAS due to sedation and seems comfortable Yes No
- Patient unable to complete VAS due to sedation and seems uncomfortable Yes No
- Patient refuses to complete VAS and seems comfortable Yes No
- Patient refuses to complete VAS and seems uncomfortable Yes No

5) Please record the lowest oxygen saturation as recorded by the pulse oximeter during the procedure (to be completed by the research coordinator) _____%

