1.3 Design and methodology

1.3.1 Research design and General Methodological Approach

We propose a randomized controlled double-blinded trial comparing oral gabapentin 600 mg to placebo among patients undergoing outpatient same-day dilation and evacuation under moderate sedation. We propose to give the study drug (gabapentin or placebo) shortly after the initiation of same-day cervical preparation and a minimum of one hour prior to D&E. The primary study outcome is maximum pain during D&E as recorded by 100-mm VAS (Table 1). Secondary outcomes include total doses of IV sedation, pain at three time points during D&E, perioperative pain, anxiety, nausea, vomiting, patient satisfaction with pain management, oxygen saturation during moderate sedation, and administration of sedation reversal agents. We will also contact patients by phone on post-operative day 1 (POD1) to assess for prolonged or delayed side effects, adverse events and overall satisfaction with pain control.

Study medications will be administered by study staff, Planned Parenthood of Metropolitan Washington DC (PPMW) staff, or MedStar Washington Hospital Center (MWHC) staff after initiation of cervical preparation. The MedStar Health Research Institute (MHRI) pharmacy will prepare identical capsules containing gabapentin 600 mg or methylcellulose placebo. The pharmacy will package the capsules in sequentially numbered opaque sealed envelopes according to a computer-generated 1:1 randomization scheme prepared by MHRI. Study staff involved in administering medications and assessing outcomes, clinical staff (health care associates, nurses, physicians), and participants will be blinded to randomization assignment. Randomization assignment will only be revealed at the time of data analysis or in the case of a serious adverse event. As there is no standard or optimal dose of pre-operative gabapentin, we have chosen to use a dose of 600 mg with the aim of maximizing pain relief while minimizing the sedative effect. This is the same dose currently being investigated during first-trimester abortion at Emory University.

Administration of analgesics, anesthetics, and anti-emetics will be standardized. Patients will generally receive the following oral pre-procedure regimen: naproxen 500 mg, ~~tramadol 50 mg,~~

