alprazolam 0.25 mg, promethazine 25 mg, and azithromycin 500 mg. Medications may be adjusted per provider judgement and patient characteristics, such as allergies. At the time of D&E, providers will administer a paracervical block using 20 mL of 1% lidocaine with 4 units vasopressin. Initial doses of moderate sedation at both sites will be 1 mg midazolam and 50 mcg fentanyl. Additional doses are sometimes required intraoperatively to achieve adequate pain relief and will be left to provider discretion. Total doses of moderate sedation will be capped at 5 mg midazolam and 200 mcg fentanyl. Total doses of midazolam and fentanyl will be documented.

Assessments and tools:

Pain will be assessed using 100-mm VAS. We will assess pre-operative pain using VAS while the patient awaits moderate sedation administration in the procedure room. We will assess intra-operative pain at the following time points: within one minute after speculum placement, within one minute after the initiation of uterine suction aspiration, and within one minute after speculum removal. An assessment of “maximum” intra-operative pain will be made 3- 5 minutes after speculum removal. VAS will be used to assess post-operative pain 30 minutes (range 20-40 minutes) after the procedure. Assessments of anxiety will be made using 20-items of state anxiety from the State Trait Anxiety Inventory (STAI), a validated tool for measurement of anxiety that is used frequently in abortion research [19], [20]. Anxiety will be assessed prior to administration of moderate sedation and 30 minutes post-procedure. Nausea, vomiting, and satisfaction with pain control will be assessed using 5-point Likert scale prior to the administration of moderate sedation and 30 minutes post-procedure. Lowest intra-operative oxygen saturation as measured via pulse oximeter and administration of reversal agents will be recorded. Adverse events will be monitored and include, but are not limited to, seizure-like activity, need for sedation reversal agent, respiratory depression (oxygen saturation <90%), use of uterotonics, aspiration of emesis, or transfer to hospital. Overall satisfaction with pain control will also be assessed on POD1 using a 5-point Likert scale. Participants will receive financial compensation in the form of a \$40 gift card on the day of the procedure for their time and participation. After completion of the phone assessment on POD1, participants will be mailed a \$10 gift card.

Table 1: Assessments

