Time	VAS	STAI	Nausea, vomiting, and satisfaction 5-point Likert
Pre: Prior to moderate sedation	X	X	X

Intra-op: Within 1 minute after speculum insertion	X		
Intra-op: Within one minute after initiating uterine aspiration	X		
Intra-op: Within 1 minute after speculum removal	X		
Max pain experienced during abortion procedure, assessed 3-5 min after speculum removal (Primary outcome)	X		
Post: 30 min after D&E completion	X	X	X
POD1			X (satisfaction only)

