1.3.3 Subject recruitment and allocation

A total of 130 participants will be recruited from two sites at the time of abortion provision: MedStar Washington Hospital Center Family Planning and Preventative Care (MWHC) and Planned Parenthood of Metropolitan Washington DC (PPMW). PPMW has a diverse patient population, with a

majority of women being African American and age 20-29 years old. We will recruit from the PPMW clinic on the day they provide second trimester termination procedures. MWHC patients are generally referred from their general obstetrician’s office or self-referred for abortion and are seen in a private outpatient office. We will recruit eligible patients on days when we are not recruiting at PPMW. Baseline characteristics of the outpatient center at WHC and at PPMW in 2012 are shown below:

Table 2: Patient demographics

Age (years)	WHC	PPMW
<20	4%	12%
20-24	11%	38%
25-29	11%	25%
30-39	68%	21%
40 or more	6%	5%
Race		
Black, non-Hispanic	22%	65%
White, non-Hispanic	61%	16%
Hispanic	11%	8%
Multiracial	0%	8%
Other/unknown	6%	3%

In both recruitment settings, D&E is offered as a same-day procedure under moderate sedation with fentanyl and midazolam. Standard care at both sites includes cervical preparation with misoprostol and/or osmotic dilators, initiated at least two hours prior to D&E. Patients will be recruited after gestational age is confirmed to be 14 through 19 weeks, after eligibility for moderate sedation is confirmed, and after patients have provided informed consent for surgical abortion (Appendix A). This occurs after the patient has completed ultrasound, counseling, lab studies, and documentation of medical history. Patients will generally be recruited after initiation of cervical preparation, as this is a time when clinic flow will not be disrupted by study recruitment. Some participants may be recruited before cervical preparation initiation, as clinic flow permits, but no participant will receive study medications until after cervical preparation has begun.

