12) Are you having an abortion because of a fetal diagnosis?

- NO
- YES. Please describe: _____

INTRODUCTION TO VISUAL ANALOG SCALE

For these questions, we are going to ask you to make an X on a line. For example, let's say you are asked how much you like Oreo cookies:

How much do you like Oreo cookies? (make an X on the line)

very little _____ very much

You answer the question by making an "X" on the line according to how much you like or dislike Oreo cookies.

If you liked Oreo cookies a lot, then you might make an "X" on the line like so:

very little _____ X _____ very much

If you liked Oreo cookies more than life itself(!), then you might make an "X" on the line like so:

very little _____ X _____ very much

If you hated Oreo cookies, then you might make an "X" like so:

very little X _____ very much

If you thought Oreo cookies were just "OK," then you might make an "X" like so:

very little _____ X _____ very much

The idea is that if you like Oreo cookies, you make an "X" on the line closer to the phrase "very much;" the closer you make the "X," the more you are saying you like Oreo cookies. If you don't like Oreo cookies, you make an "X" on the line closer to the phrase "very little;" the closer you make the "X," the more you are saying you don't like Oreo cookies.

13) How much do you like Oreo cookies? (make an X on the line)

very little _____ very much

14) How much pain do you experience with your menstrual periods? (make an X on the line)

very little _____ very much

15) How much pain do you anticipate having during your procedure? (make an X on the line)

very little _____ very much

16) How much pain you are experiencing at this time? (make an X on the line)

very little _____ very much

Medical Record Review

1) Date of birth (MM/DD/YYYY): ____ / ____ / ____

2) Gestational age: ____ weeks ____ days

3) Height: ____

4) Weight: ____ kg/lbs

5) Medications administered:

Type: (include antibiotics, misoprostol, uterotonics, pain and nausea medication)	Route -Oral -IV -Rectal -Vaginal -Paracervical	Dose	Timing - Pre-op - Intra-op - Post-op	Time	Notes
 Azithromycin	 Oral	 500 mg	 Pre		
 Alprazolam	 Oral	 0.25 mg	 Pre		

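### The item that collects the primary outcome asks about maximum pain during the abortion, with no start point, while the outcome is defined as maximum pain during D&E

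*Combined protocol and SAP*

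**What the plan says.** Objective 1 (section 1.1.2) concerns intra-operative pain during D&E. Three places describe the primary outcome:

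- Section 1.3.1, design: "The primary study outcome is maximum pain during D&E as recorded by 100-mm VAS".
- Section 1.3.1, assessments: the rating of maximum "intra-operative pain will be made 3- 5 minutes after speculum removal".
- Table 1: "Max pain experienced during abortion procedure, assessed 3-5 min after speculum removal (Primary outcome".

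The question put to the woman, in Appendix E item 4, is "What was the maximum pain you experienced during your abortion". It names no start or end of the recall period.

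On timing, section 1.3.3 describes "cervical preparation with misoprostol and/or osmotic dilators, initiated at least two hours prior to D&E" and adds that "no participant will receive study medications until after cervical preparation has begun". Section 1.3.1 places the study drug shortly after preparation starts and at least one hour before D&E. It describes paracervical block and IV sedation only at the D&E itself. Section 1.3.6 takes speculum removal as the end of the procedure.

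Another pain item in the same set of forms, Appendix C item 15, uses a different noun: "How much pain do you anticipate having during your procedure".

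**The concern.** The stated outcome covers the operation. The printed question can also be read to cover the whole same-day course, including misoprostol cramping and dilator placement. A woman whose worst pain came then could mark it in good faith, and her score would no longer measure Objective 1.

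Pain at the start of preparation comes before dosing, so gabapentin cannot change it. Preparation pain after dosing belongs to pre-operative pain, which is Objective 3. If the drug works during the D&E, preparation pain is more often the larger of the two in the gabapentin arm, which narrows the difference between arms.

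The collected data could not cleanly identify such answers. The earlier pain ratings (Appendix C item 16, Appendix D item 1) ask about current pain, not the worst pain during preparation. An item 4 score above all three timed intra-operative scores could be preparation pain, or a true peak between the timed ratings.

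**Working it through.** **Inputs from section 1.3.11.** Control mean 45, SD 25, difference 13, alpha 0.05, power 80%, 59 per arm (118 total), 130 enrolled (65 per arm at 1:1). Sidedness is not stated; two-sided reproduces the plan.

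**Inputs not in the documents (assumptions).** The share f of women who report drug-unaffected preparation pain under item 4, and the distribution of preparation pain.

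**1. The plan's own figure.** n per arm = 2 × (25/13)² × (1.960 + 0.842)² = 58.05, rounded up to 59. The t-test version gives 59.03. The plan's 59 is reproduced. Two-sample t-test power is 80.0% at 59 per arm and 83.7% at 65 per arm.

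**2. Order of events.** Preparation starts, then the study drug is given, then (at least one hour after the drug and two hours after preparation starts) the D&E. Some preparation pain is therefore pre-dose and some is post-dose.

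**3. Fixed share.** Let a share f in each arm report pain with the same mean in both arms. The expected difference is 13 × (1 − f). SD is held at 25, so the standard error is 25 × √(2/59) = 4.60 or 25 × √(2/65) = 4.39.

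| f | Difference | Power, 59 per arm | Power, 65 per arm |
|---|---|---|---|
| 0% | 13.0 | 80% | 84% |
| 5% | 12.35 | 76% | 80% |
| 10% | 11.7 | 71% | 75% |
| 20% | 10.4 | 61% | 65% |

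**4. Extreme case.** Suppose every woman marks the larger of D&E pain and preparation pain, and the drug does not affect preparation pain at all. D&E means are 45 and 32, SD 25. Preparation pain is assumed to have mean 15 to 35, SD 25, and correlation 0.3 to 0.6 with D&E pain. Scores are limited to 0–100, which by itself reduces the 13 points to 12.1. By simulation, the difference falls to between 10.5 and 6.9, and power at 65 per arm to between about 74% and 42%.

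**5. The other end.** Suppose gabapentin lowers preparation pain by the same 13 points. With X the D&E pain and Y the preparation pain, max(X − 13, Y − 13) = max(X, Y) − 13, so nothing is diluted. The simulation with scores limited to 0–100 gives about 12.5, with no loss of power.

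**6. No drug effect.** If gabapentin changes neither kind of pain, item 4 has the same distribution in both arms whichever way women read it. Type I error stays at its nominal level.

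**The case against.** The context already points to the D&E. Item 4 stands on a form headed as intra-operative. It follows ratings at speculum placement, aspiration and speculum removal, and is asked 3–5 minutes after the procedure ends by a coordinator who stays in the room (section 1.6). By then the woman has rated her current pain at baseline and again just before sedation. The protocol often uses abortion to mean the operation, and Table 1 joins the two nouns. Appendices A and B were not in the text available for review, and the content of the scheduled staff training is not shown, so a spoken explanation cannot be ruled out.

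Most of this stands, and it makes the D&E reading the likely one. But these are cues rather than a definition, and the form itself provides for women too sedated to complete the scale.

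It is also fair to object that calculations at 59 per arm overstate the loss if nearly all 130 women contribute, and that treating all preparation pain as beyond the drug's reach is one-sided. Both objections hold, so the table shows 65 per arm as well, and step 5 gives the case with no loss.

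A reader might infer that a null primary result would be explained by the wording. The documents do not support that. They give no figure for how many women would answer this way, Objective 3 expects the drug to lower pre-operative pain too, and the three timed scores offer a partial check.

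**Conclusion.** The mismatch is real: the sole item for the primary outcome is looser than the outcome it is meant to measure. This is a cheap improvement, not a defect in the sample size, which reproduces.

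The wording affects what is measured and possibly power. Dilution requires pre-dose or drug-unaffected preparation pain that exceeds the D&E pain and is reported under item 4. Its size rests wholly on the assumed f. At 65 per arm, power is about 80% for f = 5% and 65% for f = 20%, and there is no loss if the drug lowers preparation pain equally. The 42% in step 4 requires every woman to take the wide reading, which the form's context makes unlikely, so it should not be read as a forecast. A reader might also infer a false-positive risk from the wording alone; randomisation rules that out when the drug has no effect on pain.

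**What to change.** Reword item 4 so that it carries its own window, for example: *Thinking only of the procedure that has just ended, from when the speculum was placed until it was taken out, what was the maximum pain you felt? Please leave out any pain from cervical preparation earlier today.* Use the same window in Table 1.

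If enrolment has begun, record which version of the form each woman completed. Add a sensitivity analysis that takes the highest of the three timed intra-operative VAS scores as the outcome. That analysis can miss peaks between the timed ratings, so it supports the primary result and does not replace it.

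The cost is one sentence on a form and a minor amendment. No assessment, staff time or participants are added.

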Appendix F: Post-operative assessments

20-40 min after procedure completion

Subject ID:	Date:	Time:	Interviewer:
-------------	-------	-------	--------------

1) How much pain are you experiencing right now? (make an X on the line)

very little _____ very much

2) How satisfied are you with your pain relief at this time?	Very unsatisfied 1	Somewhat unsatisfied 2	Neutral 3	Somewhat satisfied 4	Very Satisfied 5
3) How much nausea are you experiencing at this time?	No nausea 1	Very little 2	Mild 3	Moderate 4	Severe nausea 5
4) How much vomiting are you experiencing at this time?	No vomiting 1	Very little 2	Mild 3	Moderate 4	Severe vomiting 5

5) Have you experienced any other symptoms, besides pain, since you were given the study medications?

- NO
 YES. If yes, please describe: _____

State Trait Anxiety Inventory (STAI) – State Items

Read each statement and select the appropriate response to indicate how you feel right now, that is, at this very moment. There are no right or wrong answers. Do not spend too much time on any one statement but give the answer which seems to describe your present feelings best.

		Not at all	A little	Somewhat	Very much so
1	I feel calm	1	2	3	4
2	I feel secure	1	2	3	4
3	I feel tense	1	2	3	4

4	I feel strained	1	2	3	4
5	I feel at ease	1	2	3	4
6	I feel upset	1	2	3	4
7	I am presently worrying over possible misfortunes	1	2	3	4
8	I feel satisfied	1	2	3	4
9	I feel frightened	1	2	3	4
10	I feel uncomfortable	1	2	3	4
11	I feel self confident	1	2	3	4
12	I feel nervous	1	2	3	4
13	I feel jittery	1	2	3	4
14	I feel indecisive	1	2	3	4
15	I am relaxed	1	2	3	4
16	I feel content	1	2	3	4
17	I am worried	1	2	3	4
18	I feel confused	1	2	3	4
19	I feel steady	1	2	3	4
20	I feel pleasant	1	2	3	4

6) Would you choose this method of pain control if you need to have this procedure again?

- NO
 YES

7) Would you recommend this method of pain control to other women who are having this procedure?

- NO
 YES

Time of discharge from recovery: ____ : ____ AM/PM

Appendix G: Post-operative day 1 assessment

Subject ID:	Date:	Time:	Interviewer:
-------------	-------	-------	--------------

8) On a scale of 1 to 5, where 1 is very unsatisfied and 5 is very satisfied, how satisfied were you with the pain relief you experienced yesterday?

- 1 very unsatisfied
- 2
- 3
- 4
- 5 very satisfied

9) Did you experience any complications or side effects yesterday or today?

- NO
- YES

If yes, please explain: _____

10) Would you choose this method of pain control if you need to have this procedure again?

- NO
- YES

11) Would you recommend this method of pain control to other women who are having this procedure?

- NO
- YES
